9.5.1 SIB total score from baseline at the Week 42 follow-up visit

Treatment differences in SIB total score from baseline at Week 42, for subjects who completed that visit, will be estimated using an ANCOVA model that will adjust for baseline SIB total scores, baseline MMSE-2 scores, age, and gender.

9.5.2 SIB total score from baseline at Week 13

An ANCOVA model as described in Section 9.5.1 will be created to estimate the difference in SIB total scores at Week 13. Again, as with the SIB difference at Week 42. The ANCOVA model will adjust for baseline SIB, baseline MMSE-2 scores, age, and gender.

9.5.3 SIB total scores from baseline at Weeks 9, 20, 24 and 30

The linear regression models using the method of GEE as described in Sections 9.4 and 9.5.2 will be used to estimate the treatment difference in mean SIB total scores from the original baseline (i.e. at screening) at Weeks 9, 20, 24 and 30. As described in Section 9.4, weighted GEE will be used to account for data that are missing at random.

9.5.4 SIB total scores from baseline at Weeks 5, 9, 15, 20, and 24 for subjects with baseline MMSE-2 scores of 10-14 and 15-18

The estimation of the treatment differences at Weeks 9, 20, 24 and 30 for patients within each MMSE-2 group will be based on GEE linear regression model utilizing SIB total scores from baseline at these five time points. As described in Section 9.4, weighted GEE will be used to account for data that are missing at random.

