6.11.4.1 SIB total score at the Week 42 follow-up visit

This endpoint will be analyzed using an Analysis of Covariance (ANCOVA) model with SIB score at Week 42 as dependent variable; treatment group as factor, and baseline SIB total score, baseline MMSE-2 score, age and gender as covariates.

6.11.4.2 The change from baseline in SIB total score at Week 13

This endpoint will be analyzed using the same ANCOVA model as described in Section 6.11.6.1.

6.11.4.3 SIB total scores from baseline at Weeks 9, 20, 24 and 30

This endpoint will be analyzed using the same MMRM model as described in Section 6.11.2 with corrections for obtaining results on corresponding visits.

6.11.4.4 SIB total scores from baseline at Weeks 9, 20, 24 and 30 for subjects with baseline MMSE-2 scores of 10-14 and 15-18

This endpoint will be analyzed using the same MMRM model as described in Section 6.11.2 with additional fixed effect for grouped baseline MMSE-2 scores (10-14 and 15-18) and corrections for obtaining results on corresponding visits.

QMD Ref: Worldwide-TMP-ST-005-7.0 Effective: 12Aug2019	Governing QMD: Worldwide-SOP-ST-001
Confidentiality Statement	
This document is the property of Worldwide Clinical Trials Inc. and may not be duplicated, copied, altered or removed from company without prior approval from Worldwide Quality Assurance or in compliance with Worldwide Standard Operating Procedures.	

Worldwide Clinical Trials Controlled Quality Management Document		
 WORLDWIDE CLINICAL TRIALS	Sponsor:	Synaptogenix, Inc.
	Protocol Number:	NTRP-101-204
STATISTICAL ANALYSIS PLAN. PHASE 2-3-4		

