6.11.4.5 Individual patient's SIB trends over time

Assessment of slopes in treatment groups and comparison of these slopes will be performed using the MMRM model for primary efficacy analysis, as it described in Section 6.11.2. This approach will be used for absolute SIB values collected from baseline over Weeks 0 to 28 as well as for changes from baseline for these time points:

```
proc mixed data = ;
  class subjid trt01pn avisitn;
  model sibdiff = VAR trt01pn avisitd trt01pn* avisitd / ddfm =
kr outpred = pred;
  repeated avisitn / type = cs subject = subjid;
  estimate "Slope, Bryostatin" time 1 time*trt_no 1 0 / cl;
  estimate "Slope, Placebo" time 1 time*trt_no 0 1 / cl;
  estimate "Slope Difference" time*trt_no 1 -1 / cl;
run;
```

Variables names:

subjid – unique number of subject,

avisitn – visit,

VAR=sib – SIB absolute total score for the first model,

VAR=sibdiff – SIB difference from baseline for the second model,

trt01pn – treatment group.

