9 CHANGES TO PLANNED PROTOCOL ANALYSIS

1. The control of false discovery rate (FDR) excluded because it was planned for the secondary (not primary) endpoints and this is a phase 2 study.
2. For the 4th secondary endpoint: <The changes from baseline at Weeks 5, 9, 13, 15, 20 and 24 in the SIB total score for subjects with baseline MMSE-2 scores of 10-14 and 15-18> the list of visits changed from Weeks 9, 15, 20 and 24 to Weeks 9, 20, 24 and 30.
3. For efficacy analysis the GEE models replaced with MMRM models as more suitable approach for analysis of longitudinal data in neurology studies.

QMD Ref: Worldwide-TMP-ST-005-7.0 Effective: 12Aug2019	Governing QMD: Worldwide-SOP-ST-001
Confidentiality Statement	
This document is the property of Worldwide Clinical Trials Inc. and may not be duplicated, copied, altered or removed from company without prior approval from Worldwide Quality Assurance or in compliance with Worldwide Standard Operating Procedures.	

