14.2.1.8	Mixed Model with Repeated Measures Analysis of Change from Baseline at week 28 in Severe Impairment Battery. Supportive Analysis: Per-Protocol Analysis Set	Stat IP	
14.2.1.9	Mixed Model with Repeated Measures Analysis of Change from Baseline at week 28 in Severe Impairment Battery. Supportive Analysis: Completers Analysis Set	Stat IP	
14.2.2	Secondary Efficacy Endpoints		
14.2.2.1	Analysis of Covariance model for Severe Impairment Battery at Week 42 follow-up visit	Stat IP	
14.2.2.2	Analysis of Covariance model for Change from Baseline of Severe Impairment Battery at Week 13	Stat IP	
14.2.2.3	Mixed Model with Repeated Measures Analysis of Changes from Baseline at weeks 9, 20, 24 and 30 in Severe Impairment Battery	Stat IP	
14.2.2.4	Mixed Model with Repeated Measures Analysis of Changes from Baseline at weeks 9, 20, 24 and 30 in Severe Impairment Battery for subjects with baseline MMSE-2 scores of 10-14 and 15-18	Stat IP	
14.2.2.5	Individual subject's trends of SIB over time	Stat IP	
14.2.2.6	Individual subject's trends of SIB changes from baseline over time	Stat IP	
14.2.3	Exploratory Endpoints		

QMD Ref: Worldwide-TMP-ST-005-7.0 Effective: 12Aug2019

Governing QMD: Worldwide-SOP-ST-001

Confidentiality Statement

This document is the property of Worldwide Clinical Trials Inc. and may not be duplicated, copied, altered or removed from company without prior approval from Worldwide Quality Assurance or in compliance with Worldwide Standard Operating Procedures.

Worldwide Clinical Trials Controlled Quality Management Document

**WORLDWIDE
CLINICAL TRIALS**

Sponsor:

Synaptogenix, Inc.

Protocol Number:

NTRP-101-204

STATISTICAL ANALYSIS PLAN. PHASE 2-3-4

Table Number	Table Title	Validation Method	Shell Number (if repeat)
14.2.3.1	Mixed Model with Repeated Measures Analysis of Change from Baseline at weeks 13 and 42 in Alzheimer’s Disease Cooperative Study – Activities of Daily Living - Severe Impairment Version	Stat IP	
14.2.3.2	Mixed Model with Repeated Measures Analysis of Change from Baseline at weeks 13 and 42 in Mini Mental State Examination, 2nd edition	Stat IP	
14.2.3.3	Mixed Model with Repeated Measures Analysis of Change from Baseline at weeks 13 and 42 in Neuropsychiatric Inventory	Stat IP	
14.3	Safety Data		
14.3.1	Displays of Adverse Events		
14.3.1.1	Overview of Adverse Events	IP	
14.3.1.2	Treatment Emergent Adverse Events	IP	
14.3.1.3	Patients with Treatment Emergent Adverse Events by Maximal Severity	IP	

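### Two secondary SIB analyses are wrong as written: the MMSE-2 subgroup model gives both groups one treatment difference, and the slope code cannot produce slopes (primary Week 28 model unaffected)

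*SAP*

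**What the plan says.** **Subgroups.** SAP 6.11.4.4 applies the model of 6.11.2 (baseline SIB, treatment, continuous visit, treatment by visit) with an "additional fixed effect for grouped baseline MMSE-2 scores (10-14 and 15-18". It names no interaction with MMSE-2 group and no separate fit per group. Protocol 9.5.4 plans to estimate "treatment differences at Weeks 9, 20, 24 and 30 for patients within each MMSE-2 group". The planned output, SAP Table 14.2.2.4, reports the "Severe Impairment Battery for subjects with baseline MMSE-2 scores of 10-14 and 15-18". For this endpoint SAP Section 9 declares only that "the list of visits changed from Weeks 9, 15, 20 and 24 to Weeks 9, 20, 24 and 30", together with the general statement "For efficacy analysis the GEE models replaced with MMRM models".

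**Slopes.** The prose of SAP 6.11.4.5 says the slopes come from the 6.11.2 model, once for absolute SIB over Weeks 0 to 28 and once for change from baseline. The code reads "model sibdiff = VAR trt01pn avisitd trt01pn* avisitd / ddfm". `VAR` is absolute SIB in the first run; for the second the SAP has "VAR=sibdiff – SIB difference from baseline for the second model". The covariance line is "repeated avisitn / type = cs subject = subjid". The ESTIMATE lines use `time` and `time*trt_no`. Protocol 9.5.5 asks for a slope for each patient from Weeks 0, 5, 9, 13, 15, 20, 24 and 28, then an average by arm and a comparison. SAP 3.2 still lists individual slopes as the endpoint.

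**The concern.** The subgroup endpoint exists to show the effect at each severity level. A model without a treatment-by-group term answers a different question and fills a two-group table with one number. Whether the effect varies with severity is a live issue: Protocol 2.1.2.4 describes different SIB patterns by MMSE-2 stratum in NTRP101-202, though with other cut-offs. SAP Section 6 gives the SAP precedence, so the protocol's wording does not repair it.

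The slope code is not merely mistyped. After the variable names are corrected, the response is still explained by itself, or by a quantity that differs from it by a constant within each patient. Someone must then choose the response, covariance, baseline term and handling of Week 0. Code and prose disagree on covariance and baseline, and neither is said to govern.

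**Working it through.** **The plan's own figure.** SAP Section 4 states power above 99%. Solving its Eq 1 for power gives Φ(√[m·n·s²·d² / (2σ²(1−ρ))] − 1.96), with n = 8, s² = 127, d = 0.15, σ = 5.3, ρ = 0.5.
- m = 50: 50·8·127·0.0225 = 1143; 2·28.09·0.5 = 28.09; √(1143/28.09) = 6.38; power above 0.999.
- m = 40 (20% dropout): √(914.4/28.09) = 5.71; power 0.9999.

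The figure reproduces. (Weeks 0 to 28 have variance 79.4, not 127; with 79.4 and m = 40 power is 0.995, so the statement survives.) Neither part below depends on it; only σ, ρ and 50 per arm are reused.

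**Subgroup algebra.** With A = 1 for bryostatin and G = MMSE-2 group, the SAP model for change at week t is

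b0 + b1·baseline + b2·A + b3·t + b4·A·t + c·G.

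Subtracting A = 0 from A = 1 leaves b2 + b4·t whether G is 0 or 1. The term c·G cancels, so the two differences are identical at every visit.

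**Size of the error.** Let group 1 have share p, balanced across arms, and let the true effects be Δ1 and Δ2 with D = Δ1 − Δ2. The model estimates p·Δ1 + (1−p)·Δ2, which is off by (1−p)·D in group 1 and p·D in group 2. For effects 4 and 0 it gives 0.5·4 = 2.0 at 50:50 and 0.3·4 = 1.2 at 30:70, for both groups. Generalised least squares fits returned those values, and 4.0 and 0.0 once the interactions were added. In 400 simulated trials with an effect of 0.30 points/week in one group and 0 in the other (50:50):

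| Week | SAP model, both groups | With interactions | Truth |
|---|---|---|---|
| 9 | 1.38 | 2.76 and about 0 | 2.7 and 0 |
| 20 | 3.05 | 6.05 and about 0 | 6.0 and 0 |
| 24 | 3.66 | 7.24 and about 0 | 7.2 and 0 |
| 30 | 4.57 | 9.03 and about 0 | 9.0 and 0 |

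**Interval cost of the interactions.** The post-baseline weeks 5, 9, 13, 15, 20, 24, 28, 30 have mean 18 and sum of squared deviations 568. Under compound symmetry and complete data the pooled variance at week t is

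(2σ²/50)·[(1 + 7ρ)/8 + (1−ρ)(t−18)²/568].

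At Week 20: 0.04·28.09·(0.5625 + 0.0035) = 0.636, half-width 1.96·0.797 = 1.56. At Week 30: 0.04·28.09·(0.5625 + 0.1268) = 0.774, half-width 1.72. Weeks 9 and 24 give 1.65 and 1.60. Within a group, multiply by 1/√share, a ratio that does not depend on σ or ρ:

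| Estimate | Factor | Half-width, Weeks 9 to 30 |
|---|---|---|
| Pooled | 1 | 1.6–1.7 |
| Each group, 50:50 | 1.41 | 2.2–2.4 |
| Smaller group, 30:70 | 1.83 | 2.9–3.1 |
| Larger group, 30:70 | 1.20 | 1.9–2.1 |

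**Slope code.**
- *Names.* The model contains `avisitd` and `trt01pn*avisitd`; the ESTIMATE lines ask for `time` and `time*trt_no`. No slope is produced.
- *Names repaired, VAR = sibdiff.* The response is its own predictor: coefficient 1, residual 0, every slope 0.
- *Names repaired, VAR = sib.* Change minus SIB is minus baseline, constant within a patient. Under compound symmetry the fit moves to a VAR coefficient of 1 with within-patient correlation near 1, and the slopes go to 0. In 400 simulated trials with true slopes 0.15 and 0, both VAR runs gave a difference of 0.000. A correctly specified model gave slopes of 0.149 and 0.003, difference 0.146 (SD 0.039).
- *Code against prose.* The code has compound symmetry and no baseline term. Section 6.11.2 has baseline SIB as covariate and tries unstructured first, then Toeplitz, then compound symmetry. With Week 0 included, an unstructured fit is singular for change from baseline (Week 0 change is always 0; rank 7 of 8) and for absolute SIB with the baseline covariate (Week 0 outcome equals the covariate; rank 7 of 8).

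**Effect of dropping Week 0.** Take a 3-point difference that is present at Week 5 and then constant (3.0 is the NTRP101-202 Week 5 FAS figure in Protocol 2.1.2.4). Weeks 0 to 28 have mean 14.25 and sum of squares 635.5, so the slope difference is 3·14.25/635.5 = 0.067 points/week. Over Weeks 5 to 28 it is 0.

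**The case against.** *Separate fits may have been intended for the subgroups.* Protocol 9.5.4 would allow that, but SAP 6.11.4.4 does not say it, and in a separate fit the added MMSE-2 term would be a redundant constant.

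*The slope error reveals itself.* This stands. A reader might infer that the trial would report a false zero slope; the more likely outcome is a program that fails and is then repaired. The point is that the repair involves open choices.

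*The prose alone may suffice.* A reader might infer that it leaves absolute SIB with no workable analysis. The documents do not support that. The 6.11.2 fallback list reaches compound symmetry. There, with Week 0 as outcome and baseline SIB as covariate, 4,000 simulated trials with no variation in patients' slopes gave a slope difference of 0.150 for a true 0.15 and a type I error of 4.6%. Toeplitz was not tried. The prose is awkward but not unworkable, and the compound symmetry in the code may be where the fallback ends.

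*Inflated type I error.* A reader might infer that keeping compound symmetry invalidates the slope test. Simulated error is about 5% if patients' slopes do not vary, 9% at a between-patient slope SD of 0.10 points/week and 23 to 24% at 0.25. The documents give no such SD, so the point does not rest on these figures.

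**Conclusion.** Both defects hold, for secondary endpoints of a Phase 2 trial. Neither enters the primary model, whose code in SAP 6.11.2 carries the baseline covariate and builds its Week 28 contrast from terms in the model. A stronger reading that reaches the primary result is not supported.

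The subgroup defect is the more serious because the program would run and return a plausible number. That both groups get the same difference is algebra and needs no assumption. The D/2 and 0.7D/0.3D errors assume the MMSE-2 split is balanced across arms, which randomization stratified by SIB does not guarantee. The documents do not give the split. The half-widths further assume σ = 5.3, ρ = 0.5, 50 per arm and complete data.

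The slope defect is a code error plus a conflict between code and prose. It should be settled before unblinding. The 6.11.2-type model also has no random slope, so even when repaired it does not yield the individual slopes named as the endpoint.

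**What to change.** **SAP 6.11.4.4.** Add MMSE-group-by-visit, treatment-by-MMSE-group and treatment-by-MMSE-group-by-visit terms, and report each group's treatment difference with its 95% CI at Weeks 9, 20, 24 and 30. A single model with shared covariance is easier to support than separate fits: an 8-visit unstructured matrix has 8·9/2 = 36 parameters, and a 30% group would have about 30 patients. The cost is the wider intervals tabulated above, which dropout will widen further.

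**SAP 6.11.4.5.** Put the outcome on the left, remove `VAR` from the right, and write the ESTIMATE lines with `avisitd` and `trt01pn*avisitd`. Keep Weeks 0 to 28 as Protocol 9.5.5 states. Obtain individual slopes in one of two ways:
- per-patient least-squares slopes compared between arms; with complete data these are identical for absolute SIB and change from baseline, since subtracting a patient's baseline does not alter the slope; or
- a random intercept and slope model of absolute SIB, with Week 0 as an outcome and no baseline covariate.

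Week 0 should not be dropped from the change slope unless SAP Section 9 declares it, because that changes the quantity estimated. State which option governs and remove the conflicting code. The whole change is a few lines of text and code and needs no new data.

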6.11.4.5 Individual patient's SIB trends over time

Assessment of slopes in treatment groups and comparison of these slopes will be performed using the MMRM model for primary efficacy analysis, as it described in Section 6.11.2. This approach will be used for absolute SIB values collected from baseline over Weeks 0 to 28 as well as for changes from baseline for these time points:

```
proc mixed data = ;
  class subjid trt01pn avisitn;
  model sibdiff = VAR trt01pn avisitd trt01pn* avisitd / ddfm =
kr outpred = pred;
  repeated avisitn / type = cs subject = subjid;
  estimate "Slope, Bryostatin" time 1 time*trt_no 1 0 / cl;
  estimate "Slope, Placebo" time 1 time*trt_no 0 1 / cl;
  estimate "Slope Difference" time*trt_no 1 -1 / cl;
run;
```

Variables names:

subjid – unique number of subject,

avisitn – visit,

VAR=sib – SIB absolute total score for the first model,

VAR=sibdiff – SIB difference from baseline for the second model,

trt01pn – treatment group.

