6.11.2 Primary Efficacy Analysis

The primary efficacy analysis will be performed using linear mixed model with repeated measures (MMRM) with SIB measured at baseline as covariate, visit treated as a continuous as well as categorical variable, treatment and treatment by visit interaction. Categorical visit will be used to identify the ordering of measurements within a subject, while continuous visit will be used as covariate alone as well as in interaction with treatment.

Week of planned visits will be used as values of categorical variable of visit. Actual study day of visits (calculated in weeks) will be used as values of continuous variable of visit. The dependent

QMD Ref: Worldwide-TMP-ST-005-7.0 Effective: 12Aug2019	Governing QMD: Worldwide-SOP-ST-001
Confidentiality Statement	
This document is the property of Worldwide Clinical Trials Inc. and may not be duplicated, copied, altered or removed from company without prior approval from Worldwide Quality Assurance or in compliance with Worldwide Standard Operating Procedures.	

Worldwide Clinical Trials Controlled Quality Management Document		
 WORLDWIDE CLINICAL TRIALS	Sponsor:	Synaptogenix, Inc.
	Protocol Number:	NTRP-101-204
STATISTICAL ANALYSIS PLAN. PHASE 2-3-4		

variable will be the change from baseline in SIB total score at weeks 5, 9, 13, 15, 20, 24, 28, and 30.

Correlation between repeated observations within a subject will be accounted for by specifying an unstructured correlation. If this model does not converge then the following covariance matrices will be used in this particular order until the model converges: Toeplitz, compound symmetry, and first-order autoregressive.

Analysis will be performed using PROC MIXED in SAS, and the resulting F-tests will be based on using Kenward-Roger’s adjusted degrees of freedom.

The treatment groups will be compared at all timepoints using a two-sided test at a 5% significance level, with the primary comparison being the difference in group means of SIB from baseline at Week 28.

The sample SAS code below implements the model detailed above with an unstructured covariance matrix (TYPE = UN in the REPEATED statement). The code assumes that AVISITN has 8 values (one for each post-baseline visit), and TRT01PN representing treatment is coded as 1 = bryostatin, 2 = placebo.

```
proc mixed data = ;
  class subjid trt01pn avisitn;
  model sibdiff = sibbase trt01pn avisitd trt01pn* avisitd /
ddfm = kr outpred = pred;

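### The slope code in SAP 6.11.4.5 enters the outcome as a covariate and names effects that are not in its model; separately, it fixes compound symmetry where its text invokes the unstructured model of 6.11.2

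*SAP*

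**What the plan says.** The text of SAP 6.11.4.5 says that the slopes will be estimated and compared "performed using the MMRM model for primary efficacy analysis, as it described in Section 6.11.2", for "absolute SIB values collected from baseline over Weeks 0 to 28 as well as for changes from baseline for these time points". In 6.11.2 the correlation within a patient "will be accounted for by specifying an unstructured correlation". If that model does not converge, Toeplitz is tried next, then compound symmetry (CS), then first-order autoregressive.

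The code under 6.11.4.5 differs from its text in three places.

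- The MODEL statement is "model sibdiff = VAR trt01pn avisitd trt01pn* avisitd", and the variable list gives "VAR=sib – SIB absolute total score for the first model" and "VAR=sibdiff – SIB difference from baseline for the second model". VAR stands where 6.11.2 has baseline SIB.
- The ESTIMATE statements use `time` and `time*trt_no`; the slope difference, for example, is "time*trt_no 1 -1 / cl". Neither `time` nor `trt_no` appears in the CLASS statement, the MODEL statement or the variable list.
- The covariance line is "repeated avisitn / type = cs subject = subjid".

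SAP Section 9 lists three changes from the protocol. None concerns the covariance or the covariates of the slope model. Protocol 9.5.5 and SAP 3.2 promise a slope for each patient, and Protocol 9.5.5 then tests the arm means against zero and against each other.

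**The concern.** Taken literally, the code cannot return the arm slopes or their difference for either outcome. Once it is repaired, the prose and the code still disagree on the covariance, and the prose does not settle two further choices.

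- **Week 0 in the change run.** The change at Week 0 is zero for everyone, so an unstructured fit that includes it is singular.
- **Baseline SIB in the absolute run.** In a run that includes Week 0, baseline is itself one of the responses.

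Unless the SAP fixes these points, the covariance, the visit set and the baseline covariate of a listed secondary endpoint will be chosen at programming. The covariance choice can change the width of the interval and the error rate of the test.

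**Working it through.** **Inputs.** SAP Section 4 gives residual SD σ = 5.3, within-patient correlation ρ = 0.5, 50 patients per arm, a two-sided 5% level and a slope difference of 0.15 points/week. Protocol 9.5.5 gives Weeks 0, 5, 9, 13, 15, 20, 24 and 28. The documents give no between-patient SD of SIB level (assumed 3.75 or 9) and no SD of patients' slopes, τ (assumed 0, 0.05, 0.10, 0.15 points/week). Data are complete throughout.

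**1. The plan's own slope figure.** SAP Equation 1 solved for power gives √[50 × 8 × 127 × 0.15² / (2 × 5.3² × 0.5)] − 1.96 = 6.38 − 1.96 = 4.42, which is 99.9995%. With 40 per arm it is 99.991%. The stated power above 99% reproduces. The listed weeks have variance 79.4 (divisor 8), not 127, but power is still 99.9% and 99.5%. The steps below use the listed weeks.

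**2. Change run as printed.** Response and covariate are the same variable. The coefficient of VAR is 1, the residual is 0, and every other coefficient is 0 (numerically, slopes below 10⁻¹⁴).

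**3. Absolute run as printed.** For patient i at visit j, sibdiff_ij = sib_ij − b_i, where b_i is that patient's baseline. Within a patient the two differ by a constant, so sib absorbs all change over time and nothing is left for the slopes.

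- Under CS the within-patient residual can be made exactly zero, so REML pushes the correlation towards 1. At correlations 0, 0.9, 0.999 and 0.9999, −2 REML log-likelihood is 4635, 2025, −1237 and −2843 (SD 3.75), and 4780, 2797, −420 and −2025 (SD 9), from one trial each.
- With a true difference of 0.15, the fitted difference at correlation 0.999 is 0.00002 (SD 3.75) or 0.0001 (SD 9), over 200 simulated trials.

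**4. ESTIMATE statements.** The model holds `avisitd` and `trt01pn*avisitd`; the statements ask for `time` and `time*trt_no`. Steps 2 and 3 apply only after these names are corrected.

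**5. Repaired, CS kept.** With the intended outcome as response and matching names, the estimated difference is 0.149 against a true 0.15. CS does not prevent slope estimation.

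**6. Error rate if CS is kept.** Let s² = 5.3² × 0.5 = 14.045, and let Sxx be the sum of squares of the visit weeks about their mean: 635.5 for Weeks 0-28 (n = 8) and 403.4 for Weeks 5-28 (n = 7).

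- True variance of a patient's slope estimate: τ² + s²/Sxx.
- Variance that CS uses: [s² + τ²·Sxx/(n − 1)]/Sxx.
- With r the ratio of the first to the second, type I error = 2·P(Z > 1.96/√r).

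Example, τ = 0.10, Weeks 0-28: r = (0.0100 + 0.0221)/[(14.045 + 0.908)/635.5] = 0.0321/0.0235 = 1.364, and 1.96/√1.364 = 1.678, giving 9.3%.

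| Assumed τ (points/week) | 0 | 0.05 | 0.10 | 0.15 |
|---|---|---|---|---|
| CS, Weeks 0-28 | 5.0% | 6.1% | 9.3% | 14.0% |
| CS, Weeks 5-28 | 5.0% | 5.7% | 7.7% | 10.8% |

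Simulation (10,000 trials per cell) gave 5.0, 6.0, 9.4 and 14.1%, and 5.0, 5.9, 6.9 and 10.8%. The 6.9% is about three Monte Carlo standard errors below the formula; a further 40,000 trials gave 7.8%. An unstructured test (no baseline covariate) stayed between 4.6% and 5.3%, and a comparison of per-patient slopes between 4.5% and 5.2%.

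**The case against.** The best case against is that this slip reveals itself. The definitions of VAR make sense only as two responses, the prose names both outcomes and the model, and the ESTIMATE lines would probably stop the program before any slope was reported. The tables also carry a validation step. That stands, and it means a false zero slope is unlikely to be reported. It does not settle the covariance, Week 0 or the baseline covariate.

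CS is also defensible. It matches the exchangeable correlation behind the power statement in SAP Section 4, it is in the 6.11.2 fallback list, and it avoids the singular unstructured fit when Week 0 is included. The SAP gives none of these as its reason, and the text still points to a model that starts from unstructured.

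A reader might infer four stronger things that the documents do not support.

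- **That CS is invalid here.** It holds 5% if patients' slopes do not vary.
- **That the inflation is an estimate for this trial.** The slope SDs are assumed. Nor does σ = 5.3 vouch for values up to 0.10. It is a residual SD, and it equals the SD of change without slope variation only because 2(1 − ρ) = 1 at ρ = 0.5. At ρ = 0.3 that SD would be 5.3 × √1.4 = 6.3, and at ρ = 0.7, 5.3 × √0.6 = 4.1.
- **That no individual slopes will be reported.** Tables 14.2.2.5 and 14.2.2.6 are titled as individual trends and their shells are not shown. Only the printed code lacks them.
- **That the primary result is at risk.** The 6.11.2 code has the right response and matching effect names.

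**Conclusion.** The printed slope code is wrong as written and should be corrected. That conclusion comes from reading the statements and needs no assumption; only the expected failure of the ESTIMATE lines is untested. The scope is one secondary endpoint whose intent can be recovered from the prose.

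The covariance mismatch is a separate, real inconsistency, and SAP Section 9 does not record it as a choice. Its size depends on how much patients' rates of change differ, which the documents do not state. The figures in the table, from 5.0% up to 14.0%, are illustrations for complete data.

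**What to change.** 1. **Responses.** Absolute run: `model sib = trt01pn avisitd trt01pn*avisitd`. Change run: `model sibdiff = sibbase trt01pn avisitd trt01pn*avisitd`.
2. **Slopes.** Write the ESTIMATE effects as `avisitd 1 trt01pn*avisitd 1 0`, `avisitd 1 trt01pn*avisitd 0 1` and `trt01pn*avisitd 1 -1`.
3. **Covariance.** Use `type=un` in both runs, with the 6.11.2 fallback order, so that code and prose agree.
4. **Record two departures in SAP Section 9.** The absolute run omits baseline SIB because baseline is its Week 0 response. The change run uses post-baseline visits to Week 28 because the Week 0 change is identically 0. The second departs from the stated Weeks 0-28, and the two runs then estimate slopes over different periods, which differ if the course is not linear.
5. **Individual slopes.** Compute and list each patient's slope and compare the arm means beside the model result in Tables 14.2.2.5 and 14.2.2.6.

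**Cost.** A few lines of code, one listing and a somewhat wider interval than under CS. If slopes do not vary, the mean 95% width is 0.122 against 0.117 points/week over Weeks 0-28, about 4% wider. At an assumed slope SD of 0.10 it is 0.147 against 0.120, or 22% wider, but there the CS interval is too narrow. These widths come from complete data without baseline SIB as covariate. The recommended change run, with baseline SIB and with dropout, was not simulated.
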